**Table 2 Clinical Laboratory Parameters for Safety Panel**

Hematology	Clinical Chemistry	Urine Analysis

 
• Hematocrit
 
• Hemoglobin
 
• Mean corpuscular hemoglobin
 
• Mean corpuscular hemoglobin concentration
 
• Mean corpuscular volume
 
• Platelet count
 
• Red blood cell count
 
• White blood cell (WBC) count
 
• Differential WBC count: 
 
• Neutrophils
 
• Basophils
 
• Eosinophils
 
• Lymphocytes
 
• Monocytes
 
 
 
	
 
• Albumin
 
• Total protein
 
• Alkaline phosphatase
 
• Alanine aminotransferase
 
• Aspartate aminotransferase
 
• Blood urea nitrogen
 
• Creatinine
 
• Gamma-glutamyl transferase
 
• Fasting glucose*
 
• Lactate dehydrogenase
 
• Potassium
 
• Sodium
 
• Total bilirubin
 
• Direct bilirubin
 
• Total cholesterol
 
• Triglycerides
 
• C-reactive protein (CRP)
 
	
 
• pH
 
• Bilirubin
 
• Glucose
 
• Nitrite
 
• Red blood cell traces
 
• Protein
 
• Specific gravity
 

\* Except at Screening where non-fasting glucose can be assessed

### 7.5.2 Serology

A test for hepatitis B (HbsAg), hepatitis C (HCV antibody) virus and human immunodeficiency virus (anti-HIV1/2) will be performed at V1. In case of positive results, the subject will be referred to appropriate medical care.

### 7.5.3 Urine Drug Screen

A urine drug screen will be performed at the site at V1 and V2. The urine will be screened for amphetamine type substances, barbiturates, benzodiazepines, cannabinoids, cocaine and opiates. In case of a positive urine drug test, a retest will not be allowed in order to evaluate eligibility. In case of an inconclusive test, a retest can be performed but this needs to be done immediately after the inconclusive test.

### 7.5.4 Urine Cotinine Screening

A urine dip-stick cotinine test will be performed at V1 and V2 in order to confirm the subject's smoking status. The test must detect cotinine with a threshold of  $\geq 200$  ng/mL, (e.g., One-Step Cotinine Test 008A086, Ultimed, Belgium). In case of a negative cotinine test, a retest will not be allowed in order to evaluate eligibility. In case of an inconclusive test, a retest can be performed but this needs to be done immediately after the inconclusive test.

### 7.5.5 Alcohol Breath Test

An alcohol breath test will be performed using an alcometer device at V1 and V2. In case of a positive alcohol test, a retest will not be allowed in order to evaluate eligibility. In case of an inconclusive test, a retest can be performed but this needs to be done immediately after the inconclusive test.

### 7.5.6 Urine Pregnancy Test

A urine pregnancy test will be performed for all female subjects at V1, V2, V4 and V6. Subjects with a positive urine pregnancy test or unclear results (from two repetitions) at V1 or V2 will not be enrolled and will be considered as screen failures. In case of any positive pregnancy test, the Investigator or designee will inform the subject about the risks associated with smoking during pregnancy.

All pregnancies detected during the study must be reported and handled as described in section 8.5. Pregnancies detected after enrollment will lead to discontinuation from the study (section 5.2).

## 7.6 Sample Handling, Storage, and Shipment

Urine drug screen, breath alcohol screen, urine pregnancy tests and urine cotinine tests will be done by the site personnel at the site. All other blood and urine samples will be managed by the laboratory designated in [Appendix B](#).

Detailed procedures for handling of samples are described in the separate sample handling manual (SHM). Safety laboratory samples will be destroyed as per laboratory local regulations. All other samples (except biobanking samples) will be destroyed post database lock or post finalization of the bioanalytical reports, whichever occurs last. The facility/-ies at which the samples are stored will be informed in writing by the Sponsor when destruction of the samples shall be performed.

### 7.6.1 Blood Samples

Blood samples will be drawn by qualified and trained site personnel. Since the test for nicotine concentration is highly sensitive, precautions should be taken during blood sampling and processing to prevent the contamination of samples with environmental nicotine. Subjects should be in a seated position during blood collection.

In total, around 238 mL of blood will be drawn for this study including samples for determination of nicotine concentrations (around 99 mL), CYP2A6 activity (8 mL), serology (5mL), safety (around 80 mL) and biobanking (about 46 mL). This calculation is based on an individual volume of each sample of 4.5 mL for nicotine PK (of which 4 mL is needed for nicotine dosing and 0.5 mL for cannula rinsing of saline solution), 4 mL for CYP2A6 analysis, 5 mL for serology, 20 mL for safety laboratory assessments and 23 mL for biobanking (5 mL for transcriptomic and 6 mL for each of the following: proteomic, lipidomic and

### Confidentiality Statement

Data and information contained in this document are considered to constitute trade secrets and confidential commercial information, and the legal protections provided to such trade secrets and confidential information are hereby claimed under the provisions of applicable law. No part of this document may be publicly disclosed without the written consent of Philip Morris Products S.A.

metabolomics). The total volume of blood drawn will not exceed the levels for a standard blood donation.

More details on the procedures for collection, labeling, handling and shipment of samples are described in the SHM/ lab manual.

### 7.6.2 Spot Urine Samples

Spot urine samples will be used for the urine drug screen, urine cotinine screen, urine pregnancy test, safety urinalysis, BoExp (NEQ, Total NNAL and CEMA) and creatinine analysis and for biobanking samples.

Spot urine for BoExp will be collected from V2-V6. Baseline values of BoExp will be assessed at V2 (Day -1) when spot urine should be collected prior to product test. At V6 (Day 29) spot urine should be collected before the start of the wash-out period.

Spot urine for biobanking will be collected at V2 (Day 1) and V6 (Day 30).

For spot urine collected for BoExp and biobanking, the time of collection as well as the total volume collected should be recorded.

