In addition to the nicotine PK assessment in plasma, exposure to nicotine during the ambulatory exposure period will be assessed by measuring urinary concentrations of nicotine equivalents (NEQ) in spot urine adjusted for creatinine. During cigarette smoking, on average 98% of the nicotine dose can be accounted for in the urine. NEQ, which is the molar sum of nicotine and five of its phase I and phase II metabolites in urine, represents more than 90% of the total dose recovered in urine (29).

Biomarkers of exposure to HPHCs found in tobacco and cigarette smoke will be measured during the study to detect reduction in the levels of these BoExp. Changes in levels of the tobacco-specific BoExp, total NNAL (30), and the BoExp to acrylonitrile, CEMA (31) which are predominantly formed during combustion of tobacco will be measured in spot urine adjusted for creatinine. Adjustment for creatinine will be performed to normalize for volume of urine excretion. As P3P is a nicotine containing product and the aerosol generated by P3P does not generate by design HPHCs other than nicotine, the levels of CEMA and total NNAL may be further used to detect cigarette use in addition to P3P use during the ambulatory exposure period and used as a chemical verification of the self-reporting.

The activity of CYP2A6 will be measured. CYP2A6 activity drives the metabolism of nicotine to cotinine and subsequent metabolites. Nicotine metabolism by CYP2A6 varies between

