### 6.2.2 Product use during confinement (V2, V6)

During the investigational period subjects will be requested to attend two on-site visits with overnight stays (with a confinement of 3-days at V2 and 2-days at V6). At the beginning of these visits, subjects will be asked to give their cigarettes and used/unused P3P products to the site staff.

Smoking cigarettes and/or use any tobacco/nicotine containing products other than P3P will not be allowed on site during the visits. On the first day of V6 (Day 29), subjects will be allowed to use P3P until the evening which will be subsequently followed by a wash-out period of at least 10 hours prior to the PK assessments which will be done on the second day of the visits. P3P use on the first day of V2 will only be allowed during the product test period (section [6.2.1](#)). P3P will be dispensed by the site staff on a product by product basis during the timeframe allowed by the protocol. The distribution should be recorded at site logs by site staff and the use of any product during the confinement days should be also recorded in the product use diary which is completed by the subject. The time of the use of the last tobacco/nicotine containing product, prior to the start of the wash-out period should be recorded.

In the morning of the second day of V2 (Day 1) and V6 (Day 30), following at least 10 hours of abstinence from any tobacco and nicotine containing products, subjects will use a single P3P product with no restrictions on the number of puffs or puffing frequency (*ad libitum* use) for a duration of up to 15 minutes. The start of product use (first puff) will be considered as  $T_0$ . The start and stop time of product use will be recorded. At V2 (Day 1), after the end of the blood sampling for PK assessments (4h after  $T_0$ ) subjects will be allowed to restart the use of

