**Table 9 Time Schedule – V3, V4, V5**

Time	Blood Sample	Procedures	Additional Information
Start of Procedure			
Beginning of the visit		Return of used and unused P3P consumables	
Beginning of the visit		Collection of spot urine for : - Pregnancy test (all female subjects) - Urinalysis safety panel - BoExp and creatinine	Pregnancy test and urinalysis safety panel only at V4.
During the visit		AE/SAE, concomitant medication recording	
During the visit		Product events malfunctions/misuse	
During the visit		Cough assessment	VAS and Likert.
During the visit		Puffing/inhalation behavior question	Answered by subjects.
During the visit	✓	Clinical laboratory parameters (hematology, clinical chemistry)	Only at V4. After at least 6 hours of fasting.
During the visit		Vital signs	After resting for at least 5 min in supine position. At least 15 min after P3P use
During the visit		ECG	After resting for at least 10 min in supine position.
During the visit		Physical examination	
During the visit		Spirometry (without bronchodilator)	After resting in sitting position for at least 15 minutes. At least

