**Table 10 Time Schedule – First day of V6 (Day 29)**

Time	Blood Sample	Procedures	Additional Information
Start of Procedure		Day 29	
Beginning of the visit		Return of used and unused P3P consumables	
Before start of nicotine wash-out		Collection of spot urine for: 
 
- Pregnancy test (all female subjects)
 
- BoExp and creatinine
 
	
		Vital signs	At least 5 min in supine position prior to measurement. At least 15 min after P3P use
		Spirometry	After resting in sitting position for at least 15 minutes. At least 1h after P3P use. To be done after vital signs.
		Cough assessment	VAS and Likert.
		Puffing/inhalation behavior question	Answered by subjects.
		Dinner	
Evening		Start of at least 10h nicotine wash-out period	

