12.5.5 Biomarkers of Exposure in Urine

Urinary concentrations adjusted for creatinine of biomarkers of exposure : Nicotine Equivalents (NEQ), total NNAL and CEMA will be considered log-normally distributed and summarized as described in section 12.1.3. The number and percent of values below LLOQ or above ULOQ will be presented in each summary table.

For each timepoint (Day 7, Day 15, Day 22, Day 29), the values and percent changes from baseline (Day -1) in the concentration adjusted for creatinine of NEQ, total NNAL and CEMA will be summarized by P3P variant, and by product use category.

The data will be presented in the below outputs:

TFL number	Title
TABLES	
15.2.19.1	Descriptive Statistics for Biomarkers of Exposure in Urine and Percent change from baseline - By Timepoint– Randomized Population
15.2.19.2	Descriptive Statistics for Biomarkers of Exposure in Urine and Percent Change from Baseline - By Timepoint – By Product Exposure Category - Randomized Population
15.2.19.3	Descriptive Statistics for Biomarkers of Exposure in Urine and Percent Change from Baseline - By Timepoint – By Sex - Randomized Population
LISTINGS	
15.1.19.1	Listing of Biomarkers of Exposure in Urine – By Timepoint - Results

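### Day 29 exposure-biomarker urine may be taken hours after arrival on a cigarette-free site, whereas V3-V5 urine is taken on arrival, so Day 29 can understate continued smoking relative to V3-V5

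*Protocol*

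**What the plan says.** **Collection times.** For V3 to V5, protocol Table 9 lists "Collection of spot urine for : - Pregnancy test (all female subjects) - Urinalysis safety panel - BoExp and creatinine" under the time heading "Beginning of the visit". For the last biomarker timepoint, section 7.6.2 states: "At V6 (Day 29) spot urine should be collected before the start of the wash-out period". Table 10 agrees: on Day 29 only product return stands under the start of the visit, and the biomarker urine stands under "Before start of nicotine wash-out". The introduction to section 9 adds that a procedure without a stated start time may be done at any time of day. SAP Table 11 sets windows for plasma nicotine samples and VAS scores but none for urine.

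**Product use on site.** Section 6.2.2 has subjects hand over their cigarettes at the start of V6 and adds: "Smoking cigarettes and/or use any tobacco/nicotine containing products other than P3P will not be allowed on site during the visits". It also says: "On the first day of V6 (Day 29), subjects will be allowed to use P3P until the evening". Between visits, smoking is discouraged but is not a reason for discontinuation (sections 5.2 and 6.2.3), so the plan foresees subjects who use both products.

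**Purpose and analysis.** Section 4.2 says "the levels of CEMA and total NNAL may be further used to detect cigarette use in addition to P3P use during the ambulatory exposure period", as a chemical check on self-report, and section 6.5.4 says much the same. SAP section 12.5.5 plans summaries "For each timepoint (Day 7, Day 15, Day 22, Day 29), the values and percent changes from baseline (Day -1"). Section 7.6.2 has the time of collection recorded, but no planned summary uses it.

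**The concern.** In a subject who still smokes, a V3-V5 void reflects the hours before arrival, which is ambulatory behaviour. A Day 29 void late in the day reflects, in part, hours in which the site prevented smoking and P3P was the only product available. Two subjects with the same smoking at home could give different Day 29 values only because one gave urine at check-in and the other before dinner.

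At stake is the use of the cigarette-derived markers to detect under-reported smoking, at the timepoint that closes the exposure period. A reader going down the rows from Day 7 to Day 29 could take a fall at the last row for reduced smoking when it reflects collection time.

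The problem is hard to repair afterwards. The documents do not ask for the time of the last cigarette before the void. The diary holds daily counts (section 7.8.1). The time logged before wash-out is that of the last tobacco or nicotine product (section 6.2.2), which on Day 29 may be P3P.

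**Working it through.** The documents state no figure on this point, and the sample size of 60 is described as empirical (protocol section 12.2). There is nothing to reproduce, so the check compares the collection conditions and then sizes the possible effect.

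**1. Conditions at each void**

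| | V3-V5 | Day 29 | Day -1 (baseline) |
|---|---|---|---|
| Collection | Start of visit | Any time before evening wash-out | After enrollment, before product test |
| Cigarettes on site | Barred | Barred | Barred from check-in |
| P3P on site before void | None expected | Allowed | None |
| Enforced cigarette-free time before void | About 0 h | 0 h up to an unstated maximum | Unstated; the later product test needs at least 4 h |

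Sources: protocol sections 6.2.1, 6.2.2, 6.6.1 and 7.6.2, and Tables 6, 9 and 10.

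**2. Day 29 relative to sampling on arrival, as at V3-V5**

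Inputs, both assumed because the documents give neither:
- h, hours on site without cigarettes before the void: 0 to 8
- t, half-life of the marker in urine: 8, 24 or 240 h

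The formula assumes a single exponential decline and no source of the marker after check-in:

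shift (%) = 100 × (2^(-h/t) - 1)

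For h = 4 and t = 8: 2^(-0.5) = 0.707, so the shift is -29.3%.

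| t | h = 0 | h = 2 | h = 4 | h = 8 |
|---|---|---|---|---|
| 8 h | 0% | -15.9% | -29.3% | -50.0% |
| 24 h | 0% | -5.6% | -10.9% | -20.6% |
| 240 h | 0% | -0.6% | -1.1% | -2.3% |

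This applies to the part of a marker that comes from cigarettes. A subject who has stopped smoking has little to lose.

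**3. Day 29 relative to Day -1**

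Let a be the cigarette-free hours before the baseline void:

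shift (%) = 100 × (2^(-(h - a)/t) - 1)

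With a = 0 the table above applies. With a = 4:

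| t | h = 0 | h = 2 | h = 4 | h = 8 |
|---|---|---|---|---|
| 8 h | +41.4% | +18.9% | 0% | -29.3% |
| 24 h | +12.2% | +5.9% | 0% | -10.9% |
| 240 h | +1.2% | +0.6% | 0% | -1.1% |

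The sign depends on whether h exceeds a, and the documents fix neither.

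**4. Nicotine equivalents**

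The formula does not apply, because P3P supplies nicotine on site. The net change depends on how on-site P3P use compares with the nicotine intake it replaces, so the direction is open.

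**5. After the change**

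Collection at the start of the visit sets h = 0, and the on-site timing difference from V3-V5 becomes 0%. Against Day -1, the h = 0 column remains. The same difference already exists at V3-V5.

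**The case against.** The strongest reply is that the bias is only possible. No Day 29 arrival time is given. The Table 10 block that holds the urine also holds spirometry, which section 7.3.9 places at arrival, so sampling on arrival is allowed and fits the schedule. The sample handling manual may say more. This stands: the protocol permits a late void but does not require one.

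Second, SAP section 12.5.5 plans no contrast of Day 29 with Days 7 to 22, only values and percent change from Day -1. This also stands. The mismatch affects reading across the rows of a descriptive table and the chemical check on self-report, not a formal test.

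Third, a reader might infer that the reduction from baseline is exaggerated. The documents do not support this. Baseline urine is also taken on site under a smoking ban, before a product test that needs at least 4 h of abstinence, so the shift can be positive, zero or negative.

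Fourth, moving Day 29 to check-in might take it further from Day -1. That is so if baseline followed a long cigarette-free interval, but V3-V5 already carry the same difference. The change makes all four post-baseline visits alike and does not create a new mismatch.

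Finally, the endpoint is secondary and descriptive, use of the markers for verification is optional, V3-V5 samples remain for it, and collection times are recorded. All true. These points limit the consequence but are no reason to keep the difference.

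**Conclusion.** The timing of Day 29 biomarker urine is not aligned with V3-V5, and a compliant late void can understate continued smoking relative to those visits for a short-lived, cigarette-derived marker. CEMA is named as the likeliest case on the assumption that its half-life lies at the short end of the range; the documents give no half-life for any of the urinary markers. With 4 to 8 h on site assumed, the fall is about 29-50% at a half-life of 8 h, 11-21% at 24 h and 1-2% at 240 h, and zero with sampling on arrival.

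Two further readings go too far. One is that all Day 29 biomarker levels are biased low: long-lived markers barely move, nicotine equivalents have no determined direction, and on-arrival sampling gives no shift. The other is that a fall as large as 65% is to be expected. That needs 12 h on site at an 8 h half-life (2^(-1.5) = 0.35), and the documents do not support so long a stay: no arrival time is stated, and dinner is the only meal in Table 10.

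This is a real but modest weakness in a secondary endpoint, worth correcting because the correction is free.

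**What to change.** In protocol section 7.6.2 and Table 10, move the Day 29 spot urine for exposure biomarkers and creatinine to the start of the visit, before any on-site P3P use, as in Table 9. The same void can serve the Day 29 pregnancy test. The cost is one line in each of two places: same sample, same day, no added procedure.

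If Day 29 samples have already been taken, add to SAP section 12.5.5 a sensitivity summary of the Day 29 values that uses the recorded collection time, for example early and late voids shown separately. State beside it that comparability with Day -1 still depends on time since the last cigarette, which neither the schedule nor the planned data fix. The cost is one extra table from data already collected.

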### 7.6.3 Biobanking

Samples of urine and whole blood/plasma will be collected at V2 and V6 for biobanking and subsequent transcriptomic, proteomic, lipidomic and metabolomic profiling as follows:

- Samples will be collected from spot urine for lipidomic profiling (2 tubes of 2 mL each per timepoint), for metabolomic profiling (4 tubes of 10 mL each per timepoint) and for proteomic profiling (4 tubes of 10 mL each per timepoint).
- Whole blood for transcriptomic (RNA) profiling (2 tubes of 2.5 mL each per time point), plasma for proteomic profiling (6 mL of whole blood at each time point to obtain and store 4 x 0.5 mL of plasma), plasma for lipidomic profiling (6 mL of whole blood at each time point to obtain and store 2 x 1 mL of plasma), and plasma for metabolomic profiling (6 mL of whole blood at each time point to obtain and store 4 x 0.5 mL of plasma) will also be collected.

All samples intended for biobanking will be kept frozen and will be shipped to a central storage facility or a bioanalytical laboratory according to the laboratory manual. Analysis of the biobanking samples will not be part of the research study report and will be reported separately. After the final RSR is signed, samples will be stored for a maximum of 10 years.

## 7.7 Questionnaires

The subject questionnaires will be completed by the subjects directly. All subject-reported outcome data as well as instructions will be provided in the subject's local language.

### Confidentiality Statement

Data and information contained in this document are considered to constitute trade secrets and confidential commercial information, and the legal protections provided to such trade secrets and confidential information are hereby claimed under the provisions of applicable law. No part of this document may be publicly disclosed without the written consent of Philip Morris Products S.A.

Symptoms or worsening of symptoms as documented on any of the questionnaires do not need to be documented as AEs because the questionnaires will be analyzed as part of the report. However, it is at the discretion of the Investigator to document such symptoms also as AEs. The main source for AE collection will be the face-to-face interview between the subject and investigational site staff using, open, non-directive questions (see section 8.2.1).

### 7.7.1 ABOUTTM-Dependence

Global dependence on tobacco and nicotine-containing products will be assessed via a subject self-reported outcome measure at V2, and at V6 using the ABOUTTM-Dependence Questionnaire (32, 38). The questionnaire includes two multi-items scales (attitudinal and behavioral) complemented by one single item assessment on urgency to use (i.e., time to first product use in the day).

Subjects will be asked to assess the questionnaire on a 5 point scale ranging:

- from “not at all” to “extremely” for the attitudinal scale;
- from “never” to “all the time” for the behavioral scale;
- from “0 to 5 minutes” to “more than 3 hours” for the urgency to use.

